8.7 Storage

Apalutamide tablets are supplied from the Janssen Pharmaceutical Companies of Johnson & Johnson in bottles of 120 tablets. Each bottle contains silica gel desiccant. The manufacturer recommends storage at 20–25°C (68–77°F); temperature excursions are permitted to 15–30°C (59–86°F). The pharmaceutical partner, CP-CTNet Lead Academic Organization, the DCP agent repository contractor, DCP Medical Monitor, and Nurse Consultant should be notified in the event of a Temperature Excursion.

8.8 Registration/Randomization

This trial will use a web-based Registration/Randomization System, developed and maintained by the CP-CTNet Data Management, Auditing, and Coordinating Center (DMACC). The Help Desk includes technical personnel and administrators of the registration programs at the Data Management Center in Amherst, NY, USA. The Help Desk is available round the clock 7 days per week, except for New Year's Eve, Memorial Day, Independence Day, Thanksgiving Day, and Christmas Day.

Frontier Science Randomization Help Desk
[name]
[contact] Extension 7301
Email: [contact]

Participants will be considered registered on the date they sign the approved informed consent document with a member of the study staff. Participants will be assigned to a dose cohort based on the sequence of registration. The study doesn't involve randomization.

Note: The Registration and Randomization process is documented in the "Stars User Guide".

8.9 Blinding and Unblinding Methods

Not applicable, this is an open-label study.

8.10 Agent Destruction/Disposal

All unused study agents and returned study bottles will be disposed according to the institutional standards.

9. CLINICAL EVALUATIONS AND PROCEDURES

9.1 Schedule of Events

Evaluation/ Procedure	Registration/Baseline (Visit 1) ¹	Agent Initiation	Agent Intervention ²	End-of-Intervention ^{1,3} (Visit 2)	Follow-Up Visit ^{1,4} (Visit 3)	Extended Follow-Up ¹⁰
Informed Consent	X					
Assess Eligibility	X					
Medical History	X					
Vital Signs/ Height and Weight	X			X ⁵		
Baseline Signs/Symptoms	X					
Karnofsky Performance Status	X					
Clinical Labs (CBC/Diff, CMP, PSA, TSH, testosterone)	X			X	X ⁶	
Blood for Plasma Apalutamide	X			X	X	
Request FFPE Tissue Slides/blocks					X	
Tobacco and Alcohol Use Assessment	X			X		
Quality of Life Questionnaire (EPIC-CP)	X			X		
COVID-19 Assessment	X			X		
Concomitant Medications	X			X ⁷	X ⁷	
Dispense Study Agent ⁸		X				
Collect Study Agent				X ⁷	X ⁷	
Review Agent Intake Calendar				X ⁷	X ⁷	
Adverse Event (AE) Review			X ⁹	X ⁷	X ⁷	X ¹⁰
Telephone Contact			X ⁹			X ¹⁰

¹ For all visits, blood draw for testosterone should occur between 7-10 AM for men < 45 years of age and prior to 2 PM for men ≥ 45 years of age. If the schedule is not feasible at Visit 1, the blood draw may be scheduled for another day.

² 4-8 weeks. Participants may receive the agent intervention up to 12 weeks if the surgery is delayed. Participants who are taken off agent may remain on study for endpoint evaluation.

³ Within 3 days prior to scheduled prostatectomy. In order to assess the plasma trough apalutamide levels, participants will be asked to hold the apalutamide dose on the day of the visit until after the blood draw.

⁴ 7-14 days post-prostatectomy unless encountering scheduling difficulties. This visit may be combined with the postoperative appointment for catheter removal.

⁵ Height required at Baseline visit only.

⁶ Testosterone and plasma apalutamide levels only. If testosterone remained elevated at Visit 3, a follow-up chart review will be conducted to capture testosterone test results if the test was repeated at the 3-month post-op standard-of-care visit.

⁷ Study agent return, AE diary return, and agent intake calendar return will occur during Visit 2 if this visit occurs the day before surgery. Otherwise, these will be done during post-op follow up. Collection of new Adverse Events and conmeds ends with the operative day.

⁸ The study drug may be delivered to the subject by study staff or contracted courier. Participant may also pick up the study agent from the clinic.

⁹ Phone contact may be substituted by text or email contact if the subject prefers. Contact will be made during the first week of agent intervention and then every 7-10 days for the duration of the study. Participants will be contacted prior to Visit 2 to remind them of the upcoming appointment and to hold that day's dose of study agent until after their blood draw.

¹⁰ Phone contact may be substituted by text or email contact if the subject prefers. Contact will be made 60 (\pm 5 days) post-prostatectomy to capture any late onset adverse events, excluding side effects that are related to prostatectomy.

9.2 Baseline Testing/Pre-Study Evaluation

At the screening/baseline visit, the informed consent form and medical records release form will be signed in order to obtain the biopsy/prostatectomy tissues, pathology reports and prior PSA test results. To minimize participant burden, remote consent may be implemented in compliance to the instructions in Appendix G. This visit will be scheduled between 7-10 AM, when feasible, for men $<$ 45 years of age and prior to 2 PM for men \geq 45 years of age because of circadian variation in testosterone levels. If the schedule is not feasible, the blood draw may be scheduled for another day. Participants will be evaluated for height, weight, and vital signs (temperature, pulse, and blood pressure), concomitant medications, medical history and baseline symptoms and signs. Baseline blood samples will be collected for CBC-diff, CMP, PSA, TSH, testosterone, and plasma apalutamide assay. Participants will also complete baseline tobacco/alcohol questionnaires and the Expanded Prostate Cancer Index Composite for Clinical Practice (EPIC-CP) questionnaire, and COVID-19 assessment. Subjects will be instructed on how to complete the Intake Calendar and Adverse Event Diary.

When eligibility is confirmed from lab results, participants will be provided with the study drug in amount sufficient for the entire study duration based on the surgery schedule and the assigned dosing regimen plus an extra week of agent supply. The study drug may be delivered to the subject by study staff or contracted courier. Participant may also pick up the study agent from the clinic.

9.3 Evaluation During Study Intervention

Participants will be contacted by phone or email during the first week of agent intervention to assess compliance and safety and then every 7-10 days for the duration of the study. Participants will be contacted prior to Visit 2 to remind them of the upcoming appointment and to hold that day's dose of study agent until after their blood draw. Participants will be contacted prior to Visit 2 to remind them of the upcoming appointment and to hold that day's dose of study agent until after their blood draw.

9.4 Evaluation at Completion of Study Intervention

Participants will be on agent intervention based on the assigned dosing regimen for 4-8 weeks. Participants may continue to receive the agent intervention for up to 12 weeks if the surgery is delayed.

Within 3 days prior to surgery (end-of-intervention visit), participants will return to the clinic for an end-of-intervention blood draw for CBC-diff, CMP, PSA, TSH, and for plasma apalutamide

assay. This visit will be scheduled between 7-10 AM, when feasible, for men < 45 years of age and prior to 2 PM for men \geq 45 years of age. Adverse events (AEs), concomitant medications (commeds) and agent compliance will be assessed. Participants will complete the follow-up tobacco/alcohol questionnaires, EPIC-CP questionnaire, and COVID-19 assessment. In order to assess the plasma trough apalutamide levels, participants will be asked to hold the apalutamide dose on the day of the visit until after the blood draw.

Study agent return, AE diary return, and agent intake calendar return will occur during the end-of-intervention visit if this visit occurs the day before surgery.

9.5 Post-intervention Follow-up Period

A blood sample will be collected 7-14 days post-prostatectomy to assess testosterone and plasma apalutamide levels. Blood draw for testosterone should occur between 7-10 AM for men < 45 years of age and prior to 2 PM for men \geq 45 years of age. This visit may be combined with the postoperative appointment for catheter removal. Study agent return, AE diary return, and agent intake calendar return will occur during this visit if not done during the end-of-intervention visit.

Participants will be contacted 60 (\pm 5 days) days post-prostatectomy by their preferred method of contact to capture any late onset adverse events, excluding side effects that are related to prostatectomy (such as erectile dysfunction, urinary incontinence, and negative sexual side effects).

At the discretion of the treating urologist, a testosterone test may be repeated at the 3-month post-surgery standard-of-care visit if the testosterone levels remained elevated at Visit 3. The testosterone results will be captured through a chart review if this was repeated at the 3-month post-op visit.

Pre-intervention biopsy and post-intervention surgical pathology reports will be collected, de-identified, labeled with study ID and participant ID and submitted to the University of Arizona Cancer Prevention Clinical Trials (UA CP-CTNet) Office.

Report Submission Information:

UA CP-CTNet Office

Attn: [name]

[name]

[name]

[contact]

[contact]

Email: [contact]

Unstained tissue slides (or tissue blocks) from the pre-intervention prostate biopsy and post-intervention prostatectomy tissue will be requested from respective pathology labs for measurement of secondary tissue biomarkers.

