1.2 Secondary Objectives

The secondary objectives, in the order of priority, are to determine the effect of low dose apalutamide on

- Reversibility of testosterone levels 7-14 days post intervention
- Post-intervention plasma trough apalutamide concentration
- Health-related quality of life.

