Beginning 1 week after MNU administration, animals received apalutamide or vehicle via oral gavage at different dosing regimens. Results showed that apalutamide is a highly potent inhibitor of prostate cancer. In the vehicle control, the incidence of invasive cancers in the dorsolateral/anterior prostate and all accessory sex cancers combined was 47% and 53%, respectively. Cancer incidence in the accessory sex glands was 0% in rats receiving either apalutamide at 30 mg/kg/day or 15 mg/kg/day. Intermittent (1 week on/1 week off) apalutamide at 30 mg/kg/day was also effective in preventing accessory sex gland cancers (10% incidence) and cancers confined to the dorsolateral/anterior prostate (3% incidence) but not as effective as the continuous daily exposure. Apalutamide was well tolerated at all dose levels (1-30 mg/kg/day). No mortality was seen in any group. Optimal pharmacodynamic activity evidenced by a dose-dependent down-regulation of androgen-dependent genes in the dorsolateral prostate was observed at the doses of 15 and 30 mg/kg/day (unpublished results from agent solicitation summary).

[figure not shown]
The clinical pharmacokinetics of apalutamide have been studied over the dose range of 30 to 480 mg/day (0.125 – 2 times the recommended dose) in the Phase I study [8]. Apalutamide was rapidly absorbed with peak plasma concentrations occurred 2 to 3 hours after administration. Maximum plasma concentration and area under the plasma concentration-time curve (AUC) increased proportionally over the dose range studied. Plasma concentrations declined slowly following dosing with a mean half-life of 3 to 4 days. Drug half-life and time to steady-state were independent of dose. Plasma trough concentration increased steadily with time and in proportion to dose. Most patients reached steady-state exposure after 3 weeks of continuous administration with the mean accumulation ratio of 5-fold.

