15.5 Secondary Objectives, Endpoints, Analysis Plans

The secondary objectives are to assess the effects of low dose apalutamide on 1) reversibility of testosterone levels 7-14 days post-intervention (post-operative), 2) post-intervention plasma trough apalutamide concentrations, and 3) health-related quality of life (HRQOL). The exploratory objectives are to determine the effects of apalutamide on intra-prostatic immune cell infiltration and Gleason score and the effects of tobacco/alcohol use on the study endpoints. The reversibility of testosterone levels will be measured by the change of testosterone levels from baseline to post operation. Paired t test will be performed on the changes in testosterone to evaluate the effects of low dose apalutamide for each dose group. Pearson correlation coefficient will be derived to evaluate the correlation between the plasma trough apalutamide levels and the change of PSA levels. HRQOL will be assessed by EPIC-CP. Changes in EPIC-CP (from baseline to end-of-intervention) in the overall score and sub-score for each measure will be derived and paired t test will be performed to evaluate the change for each dose group. Linear mixed effects model with a random intercept accounting within-subject dependence will be performed to compare the change in Gleason score of pre- and post-intervention tumor(s) since a participant can have more than one tumor. Changes in the Gleason score of pre- and post-intervention tumor(s) will also be assessed in a subgroup of participants where materials are available from pre- and post-intervention tumor(s) with matched location. The intra- prostatic immune cell infiltration will be measured by CD8⁺, CD4⁺, and CD56⁺ positive cells in the prostate tissues using immunohistochemistry. Changes (from most recent biopsy to prostatectomy) in these immune cells will be assessed for each dose group by paired t test. In addition, for changes in each of the secondary/exploratory endpoints a 95% CI will be reported for

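### Testosterone reversibility is sampled before the drug has necessarily washed out, and the plan does not use the drug level taken at the same visit to interpret it

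*Combined protocol and SAP*

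**What the plan says.** Section 1.2 lists the secondary objectives in priority order, and the first is "Reversibility of testosterone levels 7-14 days post intervention". Sections 10.2 and 15.5 make clear that the interval is post-operative.

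The sample is set in section 9.5: "A blood sample will be collected 7-14 days post-prostatectomy to assess testosterone and plasma apalutamide levels". Footnote 4 of the Schedule of Events (9.1) relaxes the window: "7-14 days post-prostatectomy unless encountering scheduling difficulties". Footnote 6 there, and sections 3 and 12.2, also put a plasma apalutamide level at this visit. The Schema's entry for Visit 3 lists a blood draw for testosterone only.

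Dosing runs up to surgery. Visit 2 falls within 3 days before the operation, and that day's tablet is held only until blood is drawn (9.4). No date for the last dose is given.

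On kinetics, section 2.2 states: "Plasma concentrations declined slowly following dosing with a mean half-life of 3 to 4 days". It adds: "Drug half-life and time to steady-state were independent of dose".

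On analysis, section 15.5 states: "The reversibility of testosterone levels will be measured by the change of testosterone levels from baseline to post operation". A paired t test follows for each dose group. Section 10.2 names two comparators, baseline and end-of-intervention. The only planned analysis of drug level correlates the trough concentration with PSA change.

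A later value is possible but optional. At the treating urologist's discretion, "a testosterone test may be repeated at the 3-month post-surgery standard-of-care visit if the testosterone levels remained elevated at Visit 3".

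**The concern.** Reversibility concerns what happens once the drug is gone. The Visit 3 clock starts at surgery, not at the last tablet, and the window opens only about two half-lives after dosing may have ended. Some men will be sampled with an appreciable amount of drug still present.

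Time since last dose also varies between men analysed together. Within the window it runs from 8 days (dose the day before surgery, sample at day 7) to 21 days (weekly dose 7 days before surgery, sample at day 14). It is longer for men who stopped the agent early and, under section 10.4, stay in follow-up for endpoint data.

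The paired t test takes no account of this. If mean testosterone at Visit 3 is above baseline, the planned result cannot be attributed: it may reflect slow recovery after the drug has gone, or drug that has not yet gone. What is at stake is the interpretation of one secondary endpoint, in one direction only.

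**Working it through.** **Inputs.** Half-life t = 3 to 4 days, independent of dose (2.2). First-day dose of three 60 mg tablets, then one tablet daily, on MWF, or weekly (7.1, 7.2). Visit 3 at 7-14 days after surgery (9.5). Assumed: first-order decay, immediate absorption, parent drug only, surgery on study days 42-48, and each man taking every scheduled dose up to the day before surgery.

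**The plan's own figures first.** Section 2.2 reports: "Most patients reached steady-state exposure after 3 weeks of continuous administration with the mean accumulation ratio of 5-fold". For once-daily dosing the accumulation ratio is 1/(1 − 2^(−1/t)), which is 4.85 at t = 3, 4.99 at t = 3.1 and 6.29 at t = 4. The share of steady state reached at 21 days is 1 − 2^(−21/t), which is 99.2% at t = 3 and 97.4% at t = 4. Both figures fit the stated half-life, so the simple model is adequate here.

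**Residual drug, in units of one tablet.** By day 42 the first-day extra (two tablets) has decayed to at most 2 × 2^(−42/4) = 0.001, so steady-state formulas apply. In each case the day-7 sample is 8 days after the last dose.

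- *Daily.* Amount just after the last dose: 1/(1 − 2^(−1/t)). Steady-state average: t/ln 2.
  - t = 3: 4.85 × 2^(−8/3) = 0.763; 0.763/4.33 = 17.6%.
  - t = 4: 6.29 × 2^(−8/4) = 1.571; 1.571/5.77 = 27.2%.
- *MWF, last dose Friday.* Amount: (1 + 2^(−2/t) + 2^(−4/t))/(1 − 2^(−7/t)). Average: (3/7)·t/ln 2.
  - t = 3: 2.529 × 2^(−8/3) = 0.398; 0.398/1.855 = 21.5%.
  - t = 4: 3.141 × 2^(−8/4) = 0.785; 0.785/2.473 = 31.7%.
- *Weekly.* Amount: 1/(1 − 2^(−7/t)). Average: (1/7)·t/ln 2.
  - t = 3: 1.248 × 2^(−8/3) = 0.196; 0.196/0.618 = 31.8%.
  - t = 4: 1.423 × 2^(−8/4) = 0.356; 0.356/0.824 = 43.2%.

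The gap from the last scheduled dose to surgery is 1 day on daily dosing, 1-3 days on MWF and 1-7 days on weekly. Over all those gaps and t = 3 to 4, the residual as a percentage of each regimen's own steady-state average is:

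| Regimen | Day 7 | Day 10, maximum | Day 14 |
|---|---|---|---|
| Daily | 17.6-27.2 | 16.2 | 3.5-8.1 |
| MWF | 13.5-31.7 | 18.9 | 2.7-9.4 |
| Weekly | 7.9-43.2 | 25.7 | 1.6-12.8 |

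The MWF maximum is a Friday dose with Saturday surgery. A Wednesday dose with Thursday surgery gives (1 + 0.7071 + 0.4204) × 1.423 × 0.25/2.473 = 30.6%, so the weekday makes little difference.

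**Another denominator.** As a share of the level just after the last dose, with that dose on the day of surgery, the residual is 2^(−7/3) = 19.8% to 2^(−7/4) = 29.7% at day 7, and 3.9% to 8.8% at day 14. The conclusion is the same: appreciable early in the window, small at its end.

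**The case against.** The strongest reply is that the protocol already collects what is needed. Plasma apalutamide is drawn with testosterone at Visit 3, and the Intake Calendar records dosing. A reader might infer that the endpoint can never distinguish non-reversal from residual drug. The documents do not support that: the data exist, and the gap is in the analysis. The ambiguity is also one-sided, since a man back at baseline with drug still present has shown reversal.

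Second, the endpoint is defined at a time. It asks whether testosterone has returned by 7-14 days after surgery, in line with the rapid decline after stopping enzalutamide cited in section 2.3. Nothing in the plan labels a raised value irreversible, and section 15.5 promises careful interpretation of the secondary endpoints. This stands, but careful interpretation of a raised value needs the drug level.

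Third, a reader might infer that carry-over would create a false difference between daily and weekly cohorts, or distort the choice of regimen. Neither follows. Under section 15.1 the second cohort is weekly or daily, never both. No between-dose test of testosterone is planned, and the dose-indicator regressions in 15.5 do not include it. Escalation, de-escalation and suitability for active-surveillance studies rest on PSA response alone.

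Fourth, residual concentration is not shown to be residual effect, because the documents give no relation between drug level and testosterone. This also stands. It is a reason to estimate that relation, and a limit on what the percentages prove.

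**Conclusion.** The point holds as a gap in the analysis plan, not as a failure of the endpoint. As planned, a raised Visit 3 testosterone is not separated from incomplete washout, although the level that would help separate them is measured at the same visit.

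The size depends on when the man is sampled. At day 7, roughly a fifth to a quarter of the steady-state average remains on daily dosing, up to about a third on MWF and up to about two-fifths on weekly. At day 14 it is under 10% for daily and MWF and at most 13% for weekly.

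These percentages rest on first-order decay and a last dose close to surgery. A man whose dosing stopped earlier carries less. They cover parent drug only: section 7.5 mentions an active metabolite, but the documents give no half-life for it. What the plan does and does not analyse is read directly from sections 10.2 and 15.5 and needs no model. The change is a cheap improvement to the first-ranked secondary endpoint; the primary analysis is unaffected.

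**What to change.** In section 15.5, keep the paired t test and add a pre-specified supportive analysis within each dose cohort:

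- Relate the testosterone change from Visit 2 to Visit 3, and from baseline to Visit 3, to Visit 3 plasma apalutamide. Days since last dose, from the Intake Calendar, is an alternative single covariate. The two are closely related, so use one and name it in advance.
- Report Visit 3 testosterone by residual drug level.
- State that a raised Visit 3 value with measurable apalutamide will not be interpreted as non-reversal, and state what the plan counts as raised and as measurable.

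Two passages also need reconciling: the Schema with sections 9.1 and 9.5 on whether Visit 3 includes a drug level, and section 10.2 with 15.5 on whether the comparator is baseline alone or baseline and end-of-intervention.

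The cost is wording only, with no new visit or sample. The drawback is precision. Each cohort has at most 20 men, and may have as few as 12 if it stops at the first evaluation, so the supportive analysis will be imprecise and the paired result will carry a qualification.

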9.6 Methods for Clinical Procedures

Blood specimens are collected by venipuncture with standard infectious disease precautionary procedures with attention to eliminating low risks to the subject including infection and bruising.

10. CRITERIA FOR EVALUATION AND ENDPOINT DEFINITION

10.1 Primary Endpoint

The primary endpoint is to determine the effects of low dose apalutamide on circulating levels of Prostate Specific Antigen (PSA). The percent change of PSA levels from baseline to end-of-intervention will be determined. If the prostate biopsy was performed within 6 weeks prior to the baseline visit, the most recent prior PSA instead of the PSA at the baseline visit will be used for the Baseline value. The proportion of participants with $\geq 25\%$ decline in PSA levels (from baseline to end-of-intervention) will be determined for each dose cohort.

